10.2.3 IMPLANT ASSESSMENT

A Transesophageal echo (TEE) should be performed within 1 hour after the index valve is implanted (from cross clamp removal) to assess placement and index valve function. The echo requirements are in the Echo Manual.

Procedural information, findings, results and device identification information to be recorded is identified in Error! Reference source not found..

Table 5 :Procedural information

General information	Clinical information	Device performance
Date of Admission	Etiology	Valve size and serial number
Date of Procedure	Diagnosis for replacement	Post-operative TEE (within 1 hour)
Implanting Surgeon	Valve implant	REFER TO ECHO MANUAL
Type of Operation	Condition of the native aortic valve	
	Sizing	
	Concomitant procedures	
	Intraoperative Adverse Events	

10.3 SUBJECT ENROLLMENT

Subjects will be considered enrolled in the clinical trial after meeting the enrollment criteria, signing the informed consent and the surgeon determines that the index valve can be implanted. The point of enrollment in the clinical trial is established in the Operating Room when the investigator confirms that the subject is an appropriate candidate for the index valve or trial device and attempts to implant the valve. Additional subjects will not be enrolled to replace those subjects implanted with the index valve who choose to withdraw from the clinical trial.

10.4 POST-PROCEDURE

10.4.1 POST-PROCEDURE CARE

At the discretion of the investigator, bioprosthetic heart valve recipients should be maintained on anticoagulant therapy (except when contraindicated) during the initial healing stages after implant, approximately 2 to 3 months in accordance with the ACC/AHA 2008 Guidelines for the Management of Patients with Valvular Heart Disease.⁶ Anticoagulants should then be discontinued over a period of 10 days, except in those patients for whom ongoing anticoagulant protection is indicated, i.e. in the absence of sinus rhythm and in patients with a dilated left atrium, calcification of the atrial wall, history of previous atrial thrombus, or any other medical condition requiring anticoagulation therapy. However, the appropriate anticoagulation therapy must be determined by the physician on an individual basis.

10.4.2 DISCHARGE

Table 6 identifies the medical information and clinical evaluation of trial subjects at discharge, which includes an echocardiogram (refer to Section 10.5).

Table 6 Discharge Information

Clinical/Physical Assessment	Blood Studies	Echocardiography (TTE)
Date of Discharge	Blood Draw Date	Date of Exam
Weight	White Blood Cell Count	REFER TO ECHO MANUAL
Heart Rate	Red Blood Cell Count	
Blood Pressure	Hemoglobin	
Cardiac Rhythm (12-lead ECG)	Hematocrit	
Anti-thromboembolic Therapy (medications)	Platelet Count	
Adverse Events	Plasma Free Hemoglobin Coagulation Profile	

Subjects, who are not discharged within 10 days post procedure must have an echocardiogram (refer to Section 10.5) to further assess placement and performance of the index valve. This echocardiogram is required to complete the evaluation of valve short-term function. Those subjects will not require an additional echocardiogram at discharge.

10.4.3 FOLLOW-UP ASSESSMENTS

Post-procedure clinical evaluation will be performed on all enrolled trial subjects at scheduled visits at the trial site. The follow-up windows are listed in **Table 7**.

Table 7: Follow-up Windows

Follow-up Assessment*	Assessment Window
3 months	± 1 month
1 year	± 1 month
2 years	± 3 month
3 years	± 3 month
4 years	± 3 month
5 years	± 3 month

*Follow-up visits are calculated from the implant date.

During each postoperative follow-up visit, the investigator(s) will determine the subject's availability for future follow-up visits. If any subject needs to be seen, at a time other than a regularly scheduled follow-up visit, due to an index device related event, the required data collection would be the same as the 1 year follow-up evaluation.

Table 8 Follow-Up Information at all Post-Discharge Visits (3 months and annually to 5 years)

Clinical/Physical Assessment	Blood Studies	Echocardiography (TTE) ³
Date of Discharge	Blood Draw Date	Years 1, 3, 5:
Physical Assessment	White Blood Cell Count	Date of exam
Cardiac Rhythm (12-lead ECG)	Red Blood Cell Count	SEE ECHO MANUAL
NYHA Classification	Hemoglobin	Years 2, 4:
Quality of Life (EQ-5D & SF12-v2) ¹	Hematocrit	Date of exam
Anti-thromboembolic Therapy (medications)	Platelet Count	Auscultation ⁴
Adverse Events	Plasma Free Hemoglobin	
	Coagulation Profile ²	

¹ Quality of Life (EQ-5D and SF12-v2) will be completed only at the 1-year follow-up visit

² Coagulation profile will be completed only at years 1, 3, and 5

³ Exam to be performed as described in the Echo Manual. Data evaluation performed by a Core Lab.

⁴ TE will be the standard echo assessment for the aortic valve but will only be completed if murmur is heard on auscultation at year 2 and year 4 interval visits.

10.5 ECHOCARDIOGRAM

Echocardiograms will be independently analyzed by the Echocardiography Core Lab. Each sonographer participating in the clinical trial must be trained on the requirements of the Echo Manual.

10.6 DEVICE REMOVAL / EXPLANT

Index valve 'removal' is the excision of the investigational valve, before implant of the investigational valve is complete, i.e., the heart is not restarted with the investigational valve in place. If the surgeon is unable to satisfactorily position or sew in the index valve, it will be removed and returned to the trial Sponsor who will provide a return valve kit. If the heart is restarted, the valve will be considered implanted and if removal is required from this point forward, it will be considered an explant.

In the event a valve is explanted, a copy of the procedure report must be provided to the trial Sponsor. Information on the cause of explant and its relationship to the valve will be provided by the investigator(s). Explanted valves must be returned to the trial Sponsor for analysis. Return kits for devices will be provided by the trial Sponsor.

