9.2 ANALYSIS POPULATION

The analyses of safety data will include all enrolled subjects. Subjects are considered enrolled in the clinical trial after meeting the enrollment criteria, signing the informed consent and the surgeon determines that the index valve can be implanted.

The analyses of performance data will include the index valve population, defined as all subjects that are enrolled into the trial and that are implanted with the index valve.

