10.8 TRIAL SUBJECT EXIT

Trial Subjects exit the trial when no additional follow-up visits, procedures, or data collection are required. A subject is exited from the trial in the following instances:

- Subject fails enrollment criteria after written consent
- Subject is considered enrolled as "intent to treat" however surgeon is unable to complete the implant procedure*
- Subject has trial device explanted*
- Subject is lost-to-follow-up
- Subject withdraws from the trial
- Subject death
- Subject completes trial follow-up

* Subjects will be followed for 30 days or until any adverse events experienced by this cohort are resolved and then will be exited from the trial.

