**** If Model 11000 is selected, please complete the following questions: ****

On what attempt was the study valve implanted?

- 1 *(If '1' is selected, please fill out one (1) Device Performance form)*
- 2 *(If '2' is selected, please fill out two (2) Device Performance forms)*

Was a post-implant echocardiogram performed? No Yes

Please complete the following questions:

Time echocardiogram started: (HH:MM)

What type of echocardiogram was done?

What was the severity of central regurgitation for the study valve?

What was the severity of paravalvular leak for the study valve?

Was observed regurgitation clinically acceptable? No Yes***** If Commercial Valve is selected, please complete the following questions: *****

After which study valve attempt was a commercial valve implanted?

- 1 *(If '1' is selected, please fill out one (1) Device Performance form (PERF).*

Why was a second attempt to implant the study valve not performed?

Please specify:

- 2 *(If '2' is selected, please fill out two (2) Device Performance forms (PERF).*

Please provide the following information about the commercial valve:

Manufacturer and Model:

Valve size: (mm)

Study

Doc#

Subject ID

Site

Visit Date

Status

Visit Name

Subevent#

CRF Name

Blank CRF

Did any adverse events occur during the surgery?

No

Yes If Yes, please ensure an adverse event form has been completed for each event.

Are the event(s) that occurred within the following AE classifications?

No Yes Blood and Lymphatic (Including ALL Bleeding complications)

No Yes Cardiovascular - Arrhythmia

No Yes Cardiovascular - Regurgitation

No Yes Cardiovascular - Stenosis

No Yes Cardiovascular - Embolic Event/Valve Thrombosis

No Yes Cardiovascular - Misc

No Yes Device Dysfunction

No Yes Gastrointestinal/Hepatic

No Yes Genitourinary/Renal

No Yes Pulmonary/Respiratory

No Yes Peripheral Vascular

No Yes Psychiatric

No Yes Muscular Skeletal/Dermatologic

No Yes Nonspecific or Unknown Body System

Study Doc#

Subject ID Site Visit Date Status

Visit Name Subevent# CRF Name Blank CRF

Was there a bleeding-related reoperation within the first 24 hours after surgery? No Yes

Please provide the times at which the following procedural steps were performed:

Start skin incision: (HH:MM)

Start ECC (Pump): (HH:MM)

Start cross clamp: (HH:MM)

Start sizing: (HH:MM)

Remove cross clamp: (HH:MM)

End ECC (Pump): (HH:MM)

End Skin closure: (HH:MM)

Comments

Study Doc#

Subject ID Site Visit Date Status

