Visit Name Subevent# CRF Name Blank CRF

DEVICE PERFORMANCE

Rev B

What study valve implant attempt was being performed?

Please provide the following information about the study valve:

Valve size:

Serial Number:

What type of sizer was used?

Please specify:

What was the barrel size of the valve sizer? mm

What suture technique was used to secure the valve?

Please specify:

How was the valve positioned?

Did the study valve perform as intended?

No

Please indicate the types of valve failures observed:

Failure type:

Please specify:

Failure type:

Please specify:

Failure type:

Please specify:

Failure type:

Please specify:

Yes

Study

Doc#

Subject ID

Site

Visit Date

Status

Visit Name

Subevent#

CRF Name

Blank CRF

DEVICE TECHNICAL SUCCESS:

Did the subject leave the operating room with the study valve in place for this attempt?

No

Why did the implant attempt fail?

Please specify:

Was the heart restarted after this implant attempt? No Yes

Yes

VALVE IMPLANT TIMES:

Start the study procedure (first stitch):

(HH:MM:SS)

Complete the study procedure (last stitch tied down on the valve):

(HH:MM:SS)

Comments

Subject ID

Site

Visit Date

Status

Visit Name

Subevent#

CRF Name

Blank CRF

DISCHARGE

Version A

Date of discharge (DD/MMM/YYYY)

Where was the subject discharged to?

Please provide the following information about the subject's hospitalization after the study valve procedure

Duration of time in the Intensive Care Unit (ICU)

Days and Hours

Duration of time in the Intermediate Care / High Dependency Unit

Days and Hours

Duration of time in the General Ward

Days and Hours

When was the transthoracic echocardiogram (TTE) performed?

Study

Doc#

Subject ID

Site

Visit Date

Status

Visit Name

Subevent#

CRF Name

Blank CRF

ADVERSE EVENT

Rev B

Event Onset Date

(DD/MMM/YYYY)

Site Awareness Date

(DD/MMM/YYYY)

Timing of Event Onset

Please select the AE Classification:

- Blood and Lymphatic (Including ALL Bleeding complications)

- Cardiovascular - Arrhythmia

- Cardiovascular - Regurgitation

- Cardiovascular - Stenosis

- Cardiovascular - Embolic Event/Valve Thrombosis

- Cardiovascular - Misc

- Device Dysfunction

- Gastrointestinal/Hepatic

- Genitourinary/Renal

- Pulmonary/Respiratory

- Peripheral Vascular

- Psychiatric

- Muscular Skeletal/ Dermatologic

- Nonspecific or Unknown Body System

Study Doc#

Subject ID Site Visit Date Status

Visit Name Subevent# CRF Name Blank CRF

Event Summary/Comments

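### A Model 11000 that cannot be seated and is removed before the heart is restarted is counted in no planned endpoint or analysis, although the case report form records it

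*Combined protocol and SAP*

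**What the plan says.** Section 10.6 defines two events. The first is "Index valve 'removal' is the excision of the investigational valve, before implant of the investigational valve is complete", which it ties to the heart not having been restarted with the valve in place. The second begins at restart: "if removal is required from this point forward, it will be considered an explant". For a failed attempt it says: "If the surgeon is unable to satisfactorily position or sew in the index valve, it will be removed and returned to the trial Sponsor". It names no endpoint or analysis for that event.

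Section 10.3 fixes enrollment during surgery, once this has happened: "the investigator confirms that the subject is an appropriate candidate for the index valve or trial device and attempts to implant the valve". A subject with a failed attempt is therefore enrolled. Section 9.2 puts all enrolled subjects in the safety analyses. The performance population is narrower: "defined as all subjects that are enrolled into the trial and that are implanted with the index valve".

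Section 7.3.1 lists 12 safety endpoints, ending with Explant. Section 7.3.2 lists 3 performance endpoints: hemodynamics, NYHA class and quality of life. Section 9.3 adds early percentages and late linearized rates for other complications. Section 9.4 covers the three performance endpoints and nothing on implant attempts.

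The case report forms in Appendix 15.3 collect the missing result. The Surgery Data form records the attempt on which the study valve was implanted and asks "After which study valve attempt was a commercial valve implanted". The Device Performance form, completed per attempt, has a technical success section asking "Did the subject leave the operating room with the study valve in place for this attempt". It goes on to the reason for failure and whether the heart was restarted.

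**The concern.** The stated purpose (7.2) is to confirm the safety and performance of this valve. Whether it can be placed is part of that. As written, a valve that had to be removed and replaced in several subjects could produce the same hemodynamic and NYHA tables, and the same Explant rate, as one that seated first time in everyone. The sponsor would hold the data to tell the two apart, but no planned result would do so.

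There is a smaller related point in the exit rules. Section 10.8 exits a subject when "Subject has trial device explanted", and the Surgery Data form allows the study valve to be implanted on a second attempt. If a first valve came out after restart and a second Model 11000 went in during the same operation, the documents do not say clearly whether that subject stays in follow-up.

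**Working it through.** The plan gives no figure to reproduce: the sample size is up to 200 with no derivation, and the documents contain no failure rate. The check is therefore mainly a comparison of definitions.

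**Step 1. Where each pathway is counted** (definitions from 9.2, 10.3 and 10.6; forms from 15.3)

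| Pathway | Explant endpoint | Performance population | Failed attempt counted in 7.3 or section 9 |
|---|---|---|---|
| Study valve placed at attempt 1 and stays | No | Yes | None to count |
| Removed before restart, second Model 11000 placed | No | Yes | No |
| Removed before restart, commercial valve or no valve | No | Never enters | No |
| Taken out after restart | Yes | Yes, it was implanted | Yes, as Explant |

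The second and third rows are the gap. In the third, the difference between the enrolled and implanted counts gives a partial signal. In the second there is no signal at all.

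**Step 2. Other routes into the results**

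- *Adverse events.* Section 11.2.1 is broad, 11.2.2 reaches device deployment and user error, and Appendix 15.1 has codes for sizing and positioning under non-structural dysfunction. That category, however, requires stenosis or regurgitation of the operated valve, or hemolysis. A removal reaches 9.3 only if a site chooses to report it, and no text requires this.
- *Device deficiencies.* Appendix 15.5 has codes for a valve that cannot be positioned on the annulus and for a sewing ring that will not take sutures. Section 9 analyses no deficiencies.
- *Table Ns.* The hemodynamic N also falls when echocardiograms are missing, because 9.6 imputes nothing. It cannot be read as an implant count.

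**Step 3. Size, for illustration only**

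Assume k of 200 enrolled subjects end without the study valve. Delivery success is (200 − k)/200, with an exact (Clopper-Pearson) interval.

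| k (assumed) | Failure, exact 95% CI | Delivery success | Maximum performance N |
|---|---|---|---|
| 0 | 0% (0 to 1.8%) | 200/200 = 100% | 200 |
| 2 | 1.0% (0.1 to 3.6%) | 198/200 = 99% | 198 |
| 4 | 2.0% (0.5 to 5.0%) | 196/200 = 98% | 196 |
| 10 | 5.0% (2.4 to 9.0%) | 190/200 = 95% | 190 |

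The Explant rate does not respond to k. With an assumed 4 explants it is 4/200 = 2.0% at every k in the table.

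For the no-trace pathway, suppose 10 first attempts fail and all 10 subjects receive a second Model 11000. The performance population is still 200 and the removals add nothing to Explant, although first-attempt success is 190/200 = 95%.

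The chance of at least one failed implant among 200 is 1 − (1 − p)^200: 63% at an assumed p of 0.5%, 87% at 1% and 98% at 2%. Unless the true rate is very low, the situation is likely to arise.

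**Step 4. The exit rule**

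- 10.6: a valve taken out after restart is an explant.
- 10.8: an explanted subject exits, after 30 days or resolution of adverse events.
- Surgery Data form: the study valve may be implanted on attempt 2.
- Device Performance form: a failed attempt is asked about heart restart.
- Footnote to the exclusion for previous implantation with the trial device (8.3, printed with 8.4): implantation is complete once the subject is off bypass and the heart is restarted.

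The footnote points against a second study valve after restart, and no passage expressly allows one. The form neither rules it out nor says what follow-up would apply.

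**The case against.** The strongest reply is that this is a descriptive, uncontrolled study with no hypothesis, so no stated analysis is wrong without the extra table. That is true. The point is an omission from the results, not an error in a calculation.

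Three stronger readings are tempting, and the documents do not support them.

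- *A failed attempt drops the subject from all endpoints.* It does not. Enrollment occurs at the attempt, safety covers all enrolled subjects, and 10.8 follows these subjects for 30 days or until adverse events resolve. Deaths, bleeding and other clinical events count, with early events over all enrolled subjects. Only the device failure itself is uncounted.
- *Restricting performance to implanted subjects is a biased choice.* Hemodynamics of the index valve exist only where the valve is in place, and a subject implanted at attempt 2 is in that population. The restriction is sound; it lacks a companion figure.
- *A removal can never be an adverse event, so the plan conceals every failure.* No text says so. A site might report one, and a report giving both 200 enrolled and, say, 196 implanted would reveal four non-implants. It would not give the reasons or show failed first attempts that were rescued.

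On the exit rule, the restart question on the form may serve only to classify removal versus explant. That is a fair reading, and it makes this part secondary.

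**Conclusion.** The concern holds for the device failure as an event. A pre-restart removal is kept out of Explant by definition, appears in 0 of 12 safety and 0 of 3 performance endpoints, and has no analysis in section 9, while the forms collect attempt number, outcome, reason and conversion. The change is worth making: the cost is small and the result bears directly on the stated purpose.

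The definitional finding rests on no assumption. The size does: 99% to 95% delivery success follows from an assumed 1% to 5% failure rate in 200 enrolled subjects, and the true rate could lie outside that range. A reader might infer that hemodynamic or NYHA results should be recalculated over all enrolled subjects. The documents give no basis for that, since a subject without the study valve has no study-valve hemodynamics.

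The exit-rule point is an unresolved inconsistency in a probably rare situation, not a demonstrated loss of follow-up.

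**What to change.** 1. Add to 7.3.2 and 9.4 a descriptive technical success result over all enrolled subjects: success at first attempt, success at second attempt, and conversion to a commercial valve or no valve. Give the recorded reasons and an exact 95% CI.
2. Show the number enrolled but not implanted beside each performance table, leaving the performance population as it is.
3. Reconcile 10.6, 10.8, the previously-implanted footnote and the two-attempt fields on whether a subject who leaves the index operation with a second study valve after an explant stays in follow-up. Confine the wording to the index operation, so that exit after a later explant is unchanged.

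The cost is one extra table from fields already on the forms and a clarification of the exit text, with no new data, visits or subjects. The downside is that a less favourable figure may be reported.

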10.7 MISSED SUBJECT VISITS

The Investigator(s) will make every attempt to follow the subjects and subjects will be encouraged by the Investigator(s) to report any address or telephone number changes to the trial site. They will also be informed of the importance of returning for scheduled follow-up visits even if they are not having any problems.

If a subject cannot be reached for a follow-up visit, the Investigator will document on the CRF, the efforts undertaken to contact the subject or the subject's primary health care provider. These efforts should include 2 attempts of telephone contact at separate dates and times, and a registered letter before the end of the follow-up window. If a subject cannot be reached for a follow-up visit, or misses a scheduled visit, the visit will be recorded as a missed visit on the date of last attempted contact. Subjects who miss a visit will not be considered withdrawn. At the next visit interval, the Investigator and/or designee will attempt to contact the subject again for follow-up. Should this attempt to contact the subject fail, a family member should be contacted in addition to the subject. Subjects who miss 2 sequential follow-up visits will be considered lost to follow-up at the second missed visit and exempt from further trial follow-up. After the subject is terminated from the trial, the Investigator will attempt to determine if the subject is alive, including searching national mortality registries as permitted by local laws.

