7 CLINICAL TRIAL DESIGN

This is a prospective, non-randomized, non-controlled, observational clinical trial. Up to 200 subjects will be enrolled at up to 6 participating trial sites. Each subject is consented for a period of 5 years. All subjects will be assessed clinically at the following intervals: Baseline, Implant, discharge, 3 months and annually to 5 years.

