Were the following interventions performed?

No Yes Valvuloplasty

No Yes Valve replacement

No Yes Other repair

Please specify:

No Yes Tricuspid valve

Were the following interventions performed?

No Yes Annuloplasty

No Yes Valvuloplasty

No Yes Valve replacement

No Yes Other repair

Please specify:

No Yes Other Cardiovascular Component

Please specify the location of the intervention and the type of surgical procedure performed

Subject ID

Site

Visit Date

Status

Visit Name

BASELINE

Subevent#

CRF Name

MEDICAL_HISTORY_P2

Blank CRF

NON-CARDIOVASCULAR RISK FACTORS

Does the subject currently have or has the subject ever had the following diseases?

 No Yes Blood Diatheses

Please specify the type:

Please specify:

 No Yes Calcium Metabolic Disorders No Yes Cancer

Please specify:

Has the subject received or will the subject receive chemotherapy within 30 days prior to the study procedure? No Yes No Yes Chronic obstructive pulmonary disease (COPD) / Chronic lung disease

Please indicate the FEV1/FVC value

What type of treatment did the subject receive for this condition?

 No Yes Chronic inhaled or oral bronchodilator therapy No Yes Chronic steroid therapy No Yes Oxygen or ventilation No Yes Other treatment

Please specify:

Subject ID

Site

Visit Date

Status

Visit Name

BASELINE

Subevent#

CRF Name

MEDICAL_HISTORY_P2

Blank CRF

No Yes Diabetes

Please indicate the type of diabetes:

Is the subject currently receiving the following treatments?

- No Yes Diet
 No Yes Oral
 No Yes Insulin

No Yes Obesity (BMI >=30)

No Yes Liver Disease

No Yes Musculoskeletal Dysfunction

Does the subject have severe impairment of mobility due to this condition? No Yes

No Yes Renal Failure/Insufficiency

Is the date when the subject was diagnosed known? No Yes

Date diagnosed

Is the approximate number of months since the subject was diagnosed known?

No Yes

Approximately how many months ago was the subject diagnosed?

Was the subject diagnosed > 5 years ago? No YesIs the subject currently on dialysis? No Yes

No Yes Other disease which requires immunosuppressive therapy inhaled or systemic steroid therapy or chemotherapy within 30 days of the study procedure

ASSESSMENT

Rev B

What was the primary method of contact with the subject?**PLEASE PROVIDE THE FOLLOWING PHYSICAL ASSESSMENT PARAMETERS:**

Weight:

 kg lb

Heart Rate:

BPM

Blood pressure:

/

mmHg

Systolic

Diastolic

NYHA Classification**Was an auscultation performed?**

- No
 Yes

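### The two-missed-visits rule ends collection of everything except vital status, even from subjects who can still be contacted or would come back

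*Combined protocol and SAP*

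**What the plan says.** Section 7 sets the horizon: "Each subject is consented for a period of 5 years", with clinical assessment at 3 months and each year to year 5. Section 10.4.3 places these visits at the trial site.

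Section 10.7 defines a missed visit with two alternative triggers: "If a subject cannot be reached for a follow-up visit, or misses a scheduled visit, the visit will be recorded as a missed visit". A single miss is expressly not a withdrawal. Two in a row are treated differently: "Subjects who miss 2 sequential follow-up visits will be considered lost to follow-up at the second missed visit and exempt from further trial follow-up". Before that point the site must telephone twice on separate occasions and send a registered letter; if the attempt at the next interval also fails, it must contact a family member. After termination one duty remains: "the Investigator will attempt to determine if the subject is alive, including searching national mortality registries as permitted by local laws".

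Section 10.8 lists "Subject is lost-to-follow-up" among the reasons for exit, and defines exit this way: "Trial Subjects exit the trial when no additional follow-up visits, procedures, or data collection are required".

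On the analysis side, section 9.3 reports late linearized rates (late events over late subject-years) and Kaplan-Meier rates for each safety endpoint. Section 9.6 uses available data without imputation. Section 9 plans no sensitivity analysis for loss to follow-up and does not say on what date a lost subject's time at risk ends.

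**The concern.** The trial follows subjects for 5 years to describe late safety and valve performance. The rule turns two absences into a permanent exit, whatever the reason for them. As written, it covers a subject who did not travel to the site twice but could still be contacted, and a subject who would have attended the next visit. Structural deterioration, thromboembolism, bleeding, endocarditis, explant, NYHA class and echo are no longer collected from that subject, although consent still runs.

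Late echo is sparse to begin with. After year 1, Table 3 schedules a routine TTE only at years 3 and 5; at years 2 and 4 it depends on a murmur. Every exit before year 5 therefore forfeits the year-5 echo, and the two earliest exits forfeit the year-3 echo as well.

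The rule also dates the loss at the second missed visit. If subject-years were run to that date, the denominator would include time in which nobody was asking about events.

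**Working it through.** **No figure to reproduce.** The documents give up to 200 subjects (section 9.1) with no derivation, and no expected miss rate, loss rate or event rate.

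**Step 1: what each missed pair forfeits** (visit schedule from section 7, rule from 10.7).

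| Pair missed | Exit at | Later visits forfeited | Years left to year 5 |
|---|---|---|---|
| 3 months, year 1 | year 1 | years 2, 3, 4, 5 | 4 |
| years 1, 2 | year 2 | years 3, 4, 5 | 3 |
| years 2, 3 | year 3 | years 4, 5 | 2 |
| years 3, 4 | year 4 | year 5 | 1 |
| years 4, 5 | year 5 | none | 0 |

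**Step 2: how many subjects, under assumed miss rates.** A subject is terminated before year 5 if two consecutive misses fall within the first five post-discharge visits. With independent misses at rate p and q = 1 − p:

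P(no such pair) = q⁵ + 5pq⁴ + 6p²q³ + p³q²

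- p = 0.10: 0.59049 + 0.32805 + 0.04374 + 0.00081 = 0.96309, so 200 × 0.03691 = 7.4 terminated.
- p = 0.05: 200 × (1 − 0.99038) = 1.9.
- p = 0.15: 200 × (1 − 0.92056) = 15.9.

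Enumerating all 2⁶ = 64 attendance patterns gives the same counts. It also shows that 1.9, 7.2 and 15.2 of these subjects (p = 5, 10, 15%) would have attended at least one later visit. The visits forfeited are 4.6, 16.9 and 34.7, or 0.4, 1.6 and 3.4% of all visits that would have been attended.

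Independence is generous to the return figure, so the enumeration was repeated with a higher miss probability after a miss:

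| Base miss rate | After a miss | Terminated of 200 | Would return later |
|---|---|---|---|
| 5% | 30% | 11.4 | 10.2 |
| 10% | 50% | 35.8 | 27.8 |
| 5% | 90% | 33.5 | 7.7 |
| 10% | 90% | 62.4 | 14.7 |

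**Step 3: effect on a late linearized rate, illustration only.** Assumptions, none from the documents: 200 subjects; late period from day 30 (0.082 years); constant 2%/year in retained subjects, all followed to year 5; 10% (20 subjects) lost after missing years 1 and 2, last seen at 3 months; twice the hazard in those lost.

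- Full follow-up: 0.9 × 2% + 0.1 × 4% = 2.20%/year over 200 × 4.918 = 983.6 subject-years.
- Retained: 180 × 4.918 = 885.2 subject-years and 885.2 × 0.02 = 17.70 events.
- Lost, time to year 2: 20 × 1.918 = 38.4, total 923.6. That is 60 subject-years fewer (6.1%).
- Events known to year 2: 38.4 × 0.04 = 1.53; (17.70 + 1.53)/923.6 = 2.08%/year.
- Events known only to month 3, time still run to year 2: 20 × 0.168 × 0.04 = 0.13; (17.70 + 0.13)/923.6 = 1.93%/year.
- Events and time both ended at month 3: 17.84/(885.2 + 3.4) = 2.01%/year.

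With equal hazards and events known to exit, the rate is 2.00 against 2.00%/year: no bias, only lost precision. With three times the hazard and events known to year 2, it is 2.17 against 2.40%/year.

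Ending time at last contact therefore repairs the denominator. Only continued collection addresses a difference in hazard.

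**The case against.** The case against has weight on five counts.

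- A reader might infer that these subjects are released from all follow-up. They are not: section 10.7 still requires an attempt to establish vital status, with a registry search where the law permits, so all-cause mortality stays partly recoverable. The section also demands real effort before loss is declared.
- A reader might infer that the plan expressly treats a subject reached by telephone as lost. It does not say whether telephone contact averts a missed visit. The Assessment form asks "What was the primary method of contact with the subject" (answer options not shown), and the deviation codes list a subject not contacted separately from an assessment outside its window. Against that, non-attendance alone is a trigger and visits are at the site. The point is an unexcepted rule plus an ambiguity, not an explicit instruction to drop contactable subjects.
- A reader might infer that the loss is always years 3 to 5. That fits one pair of the five.
- A reader might infer that those lost are sicker and that the reported rates are biased. That is plausible after valve surgery, but the documents do not say it and it cannot be sized from them.
- The trial is uncontrolled and descriptive, so no hypothesis test is at risk. If absence is highly persistent, most of those terminated would not have returned anyway (about a quarter at 90% persistence).

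All of this limits the size of the point. None of it supplies an exception for a contactable subject, a way back after two misses, or a downstream analysis that compensates.

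**Conclusion.** The concern holds in limited form. Following sections 10.7 and 10.8 as written ends non-fatal event, NYHA and echo collection after two sequential absences, including from subjects who could still be contacted or would return; vital status alone is still sought. The forfeited visits run from years 2–5 down to none.

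The number affected rests wholly on assumed miss rates: about 2, 7 or 16 of 200 at independent rates of 5, 10 or 15%, and more if misses cluster. No bias in a trial estimate is demonstrated; it needs a different event rate in those lost, or time at risk counted while events go unrecorded. Nor do the documents state that subject-years run to the second missed visit. They date the loss there and leave the end of time at risk undefined.

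This is an inexpensive improvement to a stated rule that should be made. It does not invalidate the descriptive analysis.

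**What to change.** Amend section 10.7, and the matching bullet in 10.8, so that two missed visits do not end participation:

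- Attempt contact at each remaining scheduled interval to 5 years.
- A subject who returns completes that visit in full, including echo, and events and reoperations since last contact are recorded.
- Where a subject can be contacted but cannot attend, collect adverse events, reoperation or explant, NYHA class and vital status by telephone, flagged as remotely obtained.
- Class a subject as lost only when the contact attempts already listed in 10.7 have failed, and reverse this if contact is regained.
- In section 9.3, end late subject-years and Kaplan-Meier follow-up at the last confirmed contact.

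The procedures largely exist already: 10.7 lists the contact attempts, the Assessment form has a contact-method field, and section 10.9 accepts a telephone assessment at trial termination for recently seen subjects. The cost is a short amendment and a few extra calls and letters. Events in a gap will be recalled rather than observed at a visit, and echo will not be recovered from subjects who cannot travel.
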